## 2.0 Other Related Complications

Myocardial Infarction	

Periprocedural MI  (≤72 h after the index procedure)
	
New ischemic symptoms (eg, chest pain or shortness of breath), or new ischemic signs (eg, ventricular arrhythmias, new or worsening heart failure, new ST-segment changes, hemodynamic instability, new pathological Q-waves in at least 2 contiguous leads, imaging evidence of new loss of viable myocardium or new wall motion abnormality) AND
 
Elevated cardiac biomarkers (preferable CK-MB) within 72 h after the index procedure, consisting of at least 1 sample post procedure with a peak value exceeding 15x as the upper reference limit for troponin or 5x for CK-MB. If cardiac biomarkers are increased at baseline (>99th percentile), a further increase in at least 50% post procedure is required AND the peak value must exceed the previously stated limit.

Spontaneous MI  (>72 h after the index procedure)
	
Any of the following criteria:
 
 
1) Detection of rise and/or fall of cardiac biomarkers (preferably troponin) with at least 1 value above the 99th percentile URL, together with the evidence of myocardial ischemia with at least 1 of the following:                             
 
• Symptoms of ischemia
 
• ECG changes indicative of new ischemia (new ST-T changes or new left bundle branch block (LBBB))
 
• New pathological Q-waves in at least 2 contiguous leads
 
• Imaging evidence of a new loss of viable myocardium or new wall motion abnormality
 
 
 
2) Sudden, unexpected cardiac death, involving cardiac arrest, often with symptoms suggestive of myocardial ischemia, and accompanied by presumably new ST elevation, or new LBBB, and/or evidence of fresh thrombus by coronary angiography and/or at autopsy, but death occurring before blood samples could be obtained, or at a time before the appearance of cardiac biomarkers in the blood.
 
3) Pathological findings of an acute myocardial infarction
 

## 2.0 Other Related Complications (continued)

Bleeding Complications	
Life-threatening or disabling bleeding	1) Fatal bleeding ( BARC type 5 ) OR 2) Bleeding in a critical organ, such as intracranial, intraspinal, intraocular, or pericardial necessitating pericardiocentesis, or intramuscular with compartment syndrome ( BARC type 3b and 3c ) OR 3) Bleeding causing hypovolemic shock or severe hypotension requiring vasopressors or surgery ( BARC type 3b ) OR 4) Overt source of bleeding with drop in hemoglobin $\geq 5$ g/dL or whole blood or packed red blood cells (RBCs) transfusion $\geq 4$ units* ( BARC type 3b )
Major bleeding ( BARC type 3a )	1) Overt bleeding either associated with a drop in the hemoglobin level of at least 3.0 g/dL or requiring transfusion of 2 or 3 units of whole blood/RBC, or causing hospitalization or permanent injury, or requiring surgery AND 2) Does not meet criteria of life-threatening or disabling bleeding
Minor bleeding ( BARC type 2 or 3a, depending on the severity )	Any bleeding worthy of clinical mention (eg, access site hematoma) that does not qualify as life-threatening, disabling, or major
*Given one unit of packed RBC typically will raise hemoglobin concentration by 1 g/dL, an estimated decrease in haemoglobin will be calculated; BARC: Bleeding Academic Research Consortium  ; RBC: red blood cell	

Note: With respect to blood transfusions, it is critical to acknowledge that a bleeding complication has to be the result of overt bleeding and cannot be adjudicated based on blood transfusions alone.

Acute Kidney Injury (up to 7 days post procedure)	
Stage 1	1) Increase in serum creatinine to 150%-199% (1.5-1.99 x increase compared with baseline) OR increase of $\geq 0.3$ mg/dL ( $\geq 26.4$ mmol/L) OR 2) Urine output $< 0.5$ mL/kg/h for $> 6$ but $< 12$ h
Stage 2	1) Increase in serum creatinine to 200%-299% (2.0-2.99 x increase compared with baseline) OR 2) Urine output $< 0.5$ mL/kg/h for $> 12$ but $< 24$ h
Stage 3	1) Increase in serum creatinine to $\geq 300\%$ ( $> 3$ x increase compared with baseline) OR serum creatinine of $\geq 4.0$ mg/dL ( $\geq 354$ mmol/L) with an acute increase of at least 0.5 mg/dL (44 mmol/L) OR 2) Urine output $< 0.3$ mL/kg/h for $\geq 24$ h OR 3) Anuria for $\geq 12$ h

**2.0 Other Related Complications (continued)**

Vascular Access Site and Access Related Complications	
Major vascular complication	1) Any aortic dissection, aortic rupture, annulus rupture, left ventricle perforation, or new apical aneurysm/pseudoaneurysm OR 2) Access site or access-related vascular injury (dissection, stenosis, perforation, rupture, arterio-venous fistula, pseudoaneurysm, hematoma, irreversible nerve injury, compartment syndrome, percutaneous closure device failure) leading to death, life-threatening or major bleeding, visceral ischemia, or neurological impairment OR 3) Distal embolization (noncerebral) from a vascular source requiring surgery or resulting in amputation or irreversible end-organ damage OR 4) The use of unplanned endovascular or surgical intervention associated with death, major bleeding, visceral ischemia or neurological impairment OR 5) Any new ipsilateral lower extremity ischemia documented by patient symptoms, physical exam, and/or decreased or absent blood flow on lower extremity angiogram OR 6) Surgery for access site-related nerve injury OR 7) Permanent access site-related nerve injury
Minor vascular complication	1) Access site or access-related vascular injury (dissection, stenosis, perforation, rupture, arterio-venous fistula, pseudoaneuysms, hematomas, percutaneous closure device failure) not leading to death, life-threatening or major bleeding*, visceral ischemia, or neurological impairment OR 2) Distal embolization treated with embolectomy and/or thrombectomy and not resulting in amputation or irreversible end-organ damage OR 3) Any unplanned endovascular stenting or unplanned surgical intervention not meeting the criteria for a major vascular complication OR 4) Vascular repair or the need for vascular repair (via surgery, ultrasound-guided compression, transcatheter embolization, or stent-graft)
Percutaneous closure device failure	Failure of a closure device to achieve hemostasis at the arteriotomy site leading to alternative treatment (other than manual compression or adjunctive endovascular ballooning)

\*Refer to VARCII bleeding definitions [54]

VALVE DYSFUNCTION REQUIRING REPEAT PROCEDURE
Any valve dysfunction that requires repeat procedure (eg, balloon valvuloplasty, TAVR, snare repositioning, placement of vascular plug paravalvular leak, or surgical AVR)

Note: Repeat procedures are reported on the appropriate eCRF (Surgical Intervention or Catheter Reintervention)

## 2.0 Other Related Complications (continued)

Complication	Definition
Conversion to open surgery	Conversion to open sternotomy during the TAVR procedure secondary to any procedure-related complications
Unplanned use of cardiopulmonary bypass	Unplanned use of CPB for hemodynamic support at any time during the TAVI procedure
Coronary artery obstruction	Angiographic or echocardiographic evidence of a new, partial or complete, obstruction of a coronary ostium, either by the TAV prosthesis itself, the native leaflets, calcifications, or dissection, occurring during or after the TAVR procedure.
Ventricular septal perforation	Angiographic or echocardiographic evidence of a new septal perforation during or after the TAVR procedure
Mitral valve apparatus damage or dysfunction	Angiographic or echocardiographic evidence of new damage (chordae, papillary muscle, or leaflet) to the mitral valve apparatus or dysfunction (eg, restrictions due to the TAV of the mitral valve during or after the TAVR procedure
Cardiac tamponade	Evidence of new pericardial effusion associated with hemodynamic instability and clearly related to the TAVI procedure
Prosthetic valve thrombosis	Any thrombus attached to or near an implanted valve that occludes part of the blood flow path, interferes with valve function, or is sufficiently large to warrant treatment. Valve-associated thrombus identified at autopsy in a patient whose cause of death was not valve related should not be reported as valve thrombosis.
Valve migration	After initial correct positioning, any observed movement (upward or downward) of the TAV within the aortic annulus from its initial position, with or without consequences.
Valve embolization	The TAV moves during or after deployment such that it loses contact within the aortic annulus
Ectopic valve deployment	Permanent deployment of the TAV in a location other than the aortic root
TAV in TAV deployment	Additional valve prosthesis is implanted within a previously implanted TAV because of sub-optimal device position and/or function, during or after the index procedure.
Hemolysis	Red cell destruction confirmed by lab data Minor hemolysis: No intervention required Major hemolysis: Requires intervention (eg, iron supplements, transfusion, invasive intervention).
Frame fracture	Visual evidence on radiography or at explant of loss of contact between elements (cells) of the stent. Minor frame fracture: Does not require intervention, or is not associated with prosthetic valve dysfunction. Major frame fracture: Intervention required (eg, reoperation, catheter re-intervention) or is associated with prosthetic valve dysfunction

## 2.0 Other Related Complications (continued)

### PROSTHETIC VALVE ENDOCARDITIS

Any of the following:

1) Fulfillment of the following Duke criteria for definite endocarditis [55]:

- Histologic and/or microbiologic evidence of infection at surgery or autopsy, or
- 2 major criteria, or
- 1 major criteria or 3 minor criteria, or
- 5 minor criteria

Major and minor criteria are as follows:

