#### Major Criteria:

- Blood cultures positive for Infective Endocarditis (IE)
  - Typical microorganisms consistent with IE isolated from two separate blood cultures, as noted below
    - Viridans streptococci, *Streptococcus bovis*, *Staphylococcus aureus*, or HACEK group
    - Community-acquired enterococci in the presence of a primary focus
  - Microorganisms consistent with IE isolated from persistently positive blood cultures defined as:
    - At least two positive cultures or blood samples obtained >12 hours apart, or
    - All of three, or a majority of four or more separate cultures of blood, the first and last sample obtained > one hour apart
  - Single blood culture positive for *Coxiella burnetii* or an antiphase I IG antibody titer >1:800
- **Evidence of endocardial involvement**
  - Positive results of echocardiography for IE defined as:
    - Oscillating intracardiac mass on a valve or supporting structures in the path of regurgitant jets or on implanted material in the absence of an anatomic explanation, or
    - Abscess, or
    - New partial dehiscence of a valvular prosthesis
  - New valvular regurgitation (worsening or changing or pre-existing murmur not sufficient)

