#### Minor Criteria:

- **Predisposition:** predisposing heart condition or intravenous drug use
- **Fever:** temperature >38°C
- **Vascular phenomena:** major arterial emboli, septic pulmonary infarcts, mycotic aneurysm, intracranial hemorrhage, conjunctival hemorrhages, and Janeway's lesions
- **Immunological phenomena:** glomerulonephritis, Osler's nodes, Roth's spots, and rheumatoid factor
- **Microbiological evidence:** positive blood culture but does not meet a major criterion (as noted above) or serological evidence of active infection with organism consistent with infectious endocarditis.
- **Echocardiographic findings:** consistent with IE but do not meet a major criterion as noted above

If only 1 major and 1-2 minor criteria are fulfilled, or if only 3-4 minor criteria are fulfilled, the event will be coded as "possible endocarditis"

- 2) Evidence of abscess, paravalvular leak, pus, or vegetation confirmed as secondary to infection by histological or bacteriological studies during a re-operation
- 3) Findings of abscess, pus, or vegetation involving the TAV or surgical bioprosthesis at autopsy

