#### Other TAVR-Related Complications

- 150 Conversion to open surgery
- 151 Unplanned used of CPB
- 152 Coronary artery obstruction
- 153 Ventricular septal perforation
- 154 Mitral valve apparatus damage
- 155 Cardiac tamponade
- 156 Prosthetic valve thrombosis
- 157 Valve migration
- 158 Valve embolization
- 159 Ectopic valve deployment
- 160 TAV in TAV deployment
- 161 Major hemolysis
- 162 Minor hemolysis
- 163 Prosthetic valve endocarditis: definite
- 164 Prosthetic valve endocarditis: possible
- 165 Major frame fracture
- 166 Minor frame fracture
- 167 Other TAVR-related complication

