7.9.3. Additional Outcome Measures

1. All-cause mortality at one year, and annually through 10 years

Event rate estimates will be provided at 1 year and annually thereafter up to 10 years for the attempted implant set. The outcome is descriptive including Kaplan-Meier rates and no statistical hypothesis test is specified.

2. All stroke (disabling and non-disabling) at one year, and annually through 10 years

Event rate estimates will be provided at 1 year and annually thereafter up to 10 years for the attempted implant set. The outcome is descriptive including Kaplan-Meier rates and no statistical hypothesis test is specified.

3. New permanent pacemaker implantation at 30 days

Event rate estimates will be provided at 30 days for the attempted implant set. The outcome is descriptive including Kaplan-Meier rates and no statistical hypothesis test is specified.

4. Myocardial Infraction at 30 days

Event rate estimates will be provided at 30 days for the attempted implant set. The outcome is descriptive including Kaplan-Meier rates and no statistical hypothesis test is specified.

5. Life-threatening bleeding at 30 days, one year, and annually through 10 years

Event rate estimates will be provided at 30 days, 1 year and annually thereafter up to 10 years for the attempted implant set. The outcome is descriptive including Kaplan-Meier rates and no statistical hypothesis test is specified.

6. Prosthetic valve endocarditis at 30 days, one year, and annually through 10 years

Event rate estimates will be provided at 30 days, 1 year and annually thereafter up to 10 years for the attempted implant set. The outcome is descriptive including Kaplan-Meier rates and no statistical hypothesis test is specified.

7. Prosthetic valve thrombosis at 30 days, one year, and annually through 10 years

Event rate estimates will be provided at 30 days, 1 year and annually thereafter up to 10 years for the attempted implant set. The outcome is descriptive including Kaplan-Meier rates and no statistical hypothesis test is specified.

8. Valve-related dysfunction requiring repeat procedure at 30 days, one year, and annually through 10 years

Event rate estimates will be provided at 30 days, 1 year and annually thereafter up to 10 years for the attempted implant set. The outcome is descriptive including Kaplan-Meier rates and no statistical hypothesis test is specified.

9. Repeat hospitalization for ascending aorta disease at 30 days, one year, and annually through 10 years

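### As printed, the definite-endocarditis list in Protocol Appendix V also captures every case that the same appendix tells coders to call possible

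*Protocol*

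**What the plan says.** Protocol Appendix V, section 2.0, Prosthetic Valve Endocarditis, gives three routes to the event. The first is headed "Fulfillment of the following Duke criteria for definite endocarditis". Besides histologic or microbiologic evidence at surgery or autopsy, it accepts any of three counts of criteria:

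- "2 major criteria, or"
- "1 major criteria or 3 minor criteria, or"
- "5 minor criteria"

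The other two routes are findings at re-operation and findings at autopsy.

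After the list of minor criteria, a separate instruction, which begins "If only 1 major and 1-2 minor criteria are fulfilled, or if only 3-4 minor criteria are fulfilled, the event will be coded as", sends such cases to the possible class instead. The event code list in Appendix V keeps the two classes apart: 163 is definite, and the next entry is "164 Prosthetic valve endocarditis: possible".

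The opening of Appendix V tells both the Clinical Events Committee (CEC) and the site investigators to code by these definitions. SAP 7.9.3 item 6 reports "Prosthetic valve endocarditis at 30 days, one year, and annually through 10 years" as Kaplan-Meier rates in the attempted implant set. It does not say whether code 163, code 164 or both count as the event.

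**The concern.** The second count line uses *or* where the surrounding text only makes sense with *and*. Read as printed, it sets the bar for definite endocarditis at one major criterion or three minor criteria. The lines above and below it then do no work, because anyone with two major criteria already has one, and anyone with five minor criteria already has three. The possible category also loses any territory of its own.

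Two people following the text could therefore give the same case different codes. If the Kaplan-Meier curve counts definite cases only, the printed wording can raise the rate. If it counts both classes, the split between them is still unreliable, and a single isolated major criterion enters as a definite event. The definition has to be applied consistently over ten years of follow-up.

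**Working it through.** **Inputs.** Appendix V lists 2 major criteria (positive blood cultures; evidence of endocardial involvement) and 6 minor criteria (predisposition, fever, vascular, immunological, microbiological, echocardiographic). Write M for the number of major and m for the number of minor criteria met. M runs from 0 to 2 and m from 0 to 6, giving 3 × 7 = 21 combinations. The routes that do not depend on counts (histology or microbiology, re-operation, autopsy) are left out. The documents state no figure on this point, so there is none to reproduce.

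**Rules.**

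- Definite as printed: M ≥ 2, or (M ≥ 1 or m ≥ 3), or m ≥ 5.
- Possible: (M = 1 and m = 1 or 2), or (M = 0 and m = 3 or 4). The word *only* in the note is taken to mean no further criteria.
- Definite with *and*: M ≥ 2, or (M ≥ 1 and m ≥ 3), or m ≥ 5.

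**As printed** (D = definite, P = possible, – = neither):

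| | m=0 | 1 | 2 | 3 | 4 | 5 | 6 |
|---|---|---|---|---|---|---|---|
| M=0 | – | – | – | D+P | D+P | D | D |
| M=1 | D | D+P | D+P | D | D | D | D |
| M=2 | D | D | D | D | D | D | D |

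Definite: 4 + 7 + 7 = 18. Possible: 4, namely (1,1), (1,2), (0,3) and (0,4). All 4 are also definite. The two-major and five-minor lines add 0 combinations.

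Counting which individual criteria are met gives the same answer. The possible rule covers 2×6 + 2×15 + 20 + 15 = 77 patterns, and all 77 are also definite.

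**With *and*.** Definite: 2 + 4 + 7 = 13. Possible: 4. Overlap: 0. Neither: 21 − 13 − 4 = 4, namely (0,0), (0,1), (0,2) and (1,0). Each line now has a function:

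- The two-major line alone supplies (2,0), (2,1) and (2,2).
- The mixed line alone supplies (1,3) and (1,4).
- The five-minor line alone supplies (0,5) and (0,6).

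Five combinations cease to be definite (18 − 13): (1,0), (1,1), (1,2), (0,3) and (0,4). The last four become possible only.

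**Giving the possible note precedence over the printed list.** Definite: 18 − 4 = 14, and the overlap disappears. But (1,0) remains definite while (1,1) and (1,2) are only possible, and (1,3) is definite again. A subject whose sole finding is "New valvular regurgitation (worsening or changing or pre-existing murmur not sufficient") would be definite, and adding a fever would downgrade the case to possible. A classification should not fall as evidence accumulates.

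**Deleting the mixed line.** Definite: 2 + 2 + 7 = 11, with no overlap. But (1,3) and (1,4) then belong to neither class.

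**The case against.** The best defence is that the note on possible endocarditis is later, more specific and directive, so an ordinary reader would treat it as a carve-out that settles all four overlapping combinations. That reading is reasonable, but it is an inference, because neither document states it. It also leaves the reversal at one major and no minor criteria. If the implanted valve itself counted as a predisposing heart condition, which the appendix does not say, the no-minor case would be rare in implanted subjects. An implanted subject with one major criterion and nothing else would then sit at (1,1), inside the overlap.

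A second defence is that experienced adjudicators know the criteria, and that Protocol section 11.1 bases the safety analysis on CEC-adjudicated events. Central adjudication does reduce the effect of disagreement between sites. The CEC is nevertheless told to use the same text. Endocarditis is also listed under other related complications rather than under safety endpoint definitions, so its mandatory adjudication is likely but not explicit.

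Third, Appendix V defines the event through definite criteria, re-operation or autopsy, which suggests that possible cases are not meant to count in outcome 6. That partly answers the silence in the SAP, so a clarifying sentence there is optional.

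Finally, the 21-combination grid shows logical overlap and nothing about how often it will occur. That is correct, and the counts should not be read as a measure of impact.

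**Conclusion.** The definition is wrong as written. Every combination assigned to possible endocarditis (4 of 4) also meets the printed definite list, and no reading of the printed words gives a coherent ordering. The appendix itself points to *and*: that reading removes every overlap, gives each line a purpose, and places the possible category immediately below the thresholds of one major with three minor criteria and of five minor criteria.

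The consequence is limited. It concerns one of 13 additional outcomes, which is descriptive and untested, and neither primary endpoint is touched. No shift in the endocarditis rate can be estimated, because the documents give neither an expected frequency nor a split between definite and possible. For scale only, one reclassified subject among 150 is 1/150 = 0.67 percentage points as a crude proportion. The counts assume two major and six minor criteria as listed, and set aside the routes that do not depend on counting.

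**What to change.** In Protocol Appendix V, section 2.0, change the mixed line to one major criterion *and* three minor criteria, after checking it against the source the protocol cites for the criteria (reference 55). The note on possible endocarditis can then stand unchanged. Do not simply delete the line, since that leaves one major with three or four minor criteria unclassified.

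If any endocarditis events have already been coded under the printed wording, re-check their assignment to 163 or 164.

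Optionally, add a sentence to SAP 7.9.3 item 6 stating that definite cases are counted and possible cases are listed separately.

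The cost is one word in the protocol and a review of any events already coded.

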#### Major Criteria:

- Blood cultures positive for Infective Endocarditis (IE)
  - Typical microorganisms consistent with IE isolated from two separate blood cultures, as noted below
    - Viridans streptococci, *Streptococcus bovis*, *Staphylococcus aureus*, or HACEK group
    - Community-acquired enterococci in the presence of a primary focus
  - Microorganisms consistent with IE isolated from persistently positive blood cultures defined as:
    - At least two positive cultures or blood samples obtained >12 hours apart, or
    - All of three, or a majority of four or more separate cultures of blood, the first and last sample obtained > one hour apart
  - Single blood culture positive for *Coxiella burnetii* or an antiphase I IG antibody titer >1:800
- **Evidence of endocardial involvement**
  - Positive results of echocardiography for IE defined as:
    - Oscillating intracardiac mass on a valve or supporting structures in the path of regurgitant jets or on implanted material in the absence of an anatomic explanation, or
    - Abscess, or
    - New partial dehiscence of a valvular prosthesis
  - New valvular regurgitation (worsening or changing or pre-existing murmur not sufficient)

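### The enterococcus line in the Appendix V endocarditis criteria appears to contain an inverted word and should be checked against its cited source

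*Protocol*

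**What the plan says.** Protocol Appendix V, section 2.0, defines prosthetic valve endocarditis through the Duke criteria, citing reference 55, and then sets out major and minor criteria. The introduction to the appendix tells both the Clinical Events Committee (CEC) and the sites to code from these definitions. The code list separates definite (163) from possible (164) endocarditis.

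Blood cultures can be a major criterion by two routes that matter here.
- **Typical organisms in two separate cultures.** One entry is "Community-acquired enterococci in the presence of a primary focus".
- **Persistent growth.** This is introduced as "Microorganisms consistent with IE isolated from persistently positive blood cultures defined as", followed by two options. The first is "At least two positive cultures or blood samples obtained >12 hours apart". The second is all of three cultures, or most of four or more, with the first and last more than an hour apart.

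A positive culture that meets no major criterion counts as one minor criterion.

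SAP section 7.9.3, item 6, reports "Prosthetic valve endocarditis at 30 days, one year, and annually through 10 years" as a Kaplan-Meier rate in the attempted implant set.

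**The concern.** The list exists to decide whether a bacteraemia should be attributed to the valve. In ordinary usage a primary focus is an identified source of infection elsewhere in the body. The entry therefore gives major weight to an enterococcal bacteraemia that already has an explanation, and only minor weight to one that has none. A source elsewhere makes the valve a less likely origin, so the weighting looks the wrong way round.

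If coders follow the text, some bacteraemias from another source would be coded too high and some unexplained ones too low. Endocarditis is followed for 10 years in 150 subjects, so a few coding decisions could be visible in the reported rate.

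**Working it through.** **Comparison within the protocol.** No second passage states the enterococcus rule, so the check is against the logic of related criteria.
- The echocardiographic major criterion in the same list counts a mass on a valve, "or on implanted material in the absence of an anatomic explanation". An alternative explanation removes the finding.
- The baseline endocarditis definition in Appendix III (STS Factors) counts the signs it marks with an asterisk only where nothing else accounts for them.

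Both discount a finding that has another explanation. The enterococcus entry does the opposite, and no rationale is given.

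**Which cases the entry decides.** The persistent-growth route has no condition on a focus. The entry therefore matters only for enterococcal cultures that miss that route: positives no more than 12 hours apart that are also not all of three, or most of four or more, spanning over an hour. The 12-hour option can also be parsed so that the interval applies only to *blood samples*. Any two positive cultures would then qualify, and the entry would have no effect.

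**Effect on the class.** Inputs are the major, minor, definite and possible rules in Appendix V. I assume that every subject meets the predisposition criterion by having a prosthetic valve. The other findings are fever (F), vascular (V) and immunological (I), each absent or present, and echo, which is none, minor or major. That gives 2 × 2 × 2 × 3 = 24 combinations.

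Write k = F + V + I + (1 if echo is minor).
- Culture scored as major: majors = 1 + (1 if echo is major); minors = 1 + k.
- Culture scored as minor: majors = (1 if echo is major); minors = 2 + k.

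The mixed rule for definite endocarditis is printed as "1 major criteria or 3 minor criteria, or". The rule for possible endocarditis covers one major with one or two minors, or three to four minors. The two rules overlap unless the printed *or* means *and*, so both readings were run.

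*Reading as one major and three minor:*

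| Other findings | Combinations | Culture major | Culture minor |
|---|---|---|---|
| Echo not major, k = 2 | 3 + 3 = 6 | definite (1 major, 3 minor) | possible (4 minor) |
| Echo not major, k = 0 | 1 | possible (1 major, 1 minor) | none (2 minor) |
| Echo major, k = 0 | 1 | definite (2 major) | possible (1 major, 2 minor) |

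The total is 6 + 1 + 1 = 8 of 24. Replacing *presence* by *absence* lowers the class in these 8 when there is a focus and raises it in the same 8 when there is none.

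*Literal* or, *with definite taking precedence where the two rules overlap:* only k = 0 without an echo major changes, from definite (one major suffices) to none (two minors). That is 1 of 24 with a focus and 1 of 24 without.

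**Effect on the endocarditis rate.** The protocol and SAP do not say whether code 163 alone or 163 and 164 together make an event.
- Under the *and* reading, if only 163 counts, 7 of the 8 changes matter, because they cross between definite and possible. If both count, only the one between possible and none matters.
- Under the literal *or*, the single change crosses between definite and none and matters either way.

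Where a shift does change whether an event is counted, one subject of 150 is 1/150 = 0.67 percentage point before censoring.

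**The case against.** The strongest reply is that the inversion is not proven. The text of reference 55 is not in the documents, *primary focus* is not defined, and the echo and baseline wording are analogies, not conflicting statements of the same rule. That stands. It is why the remedy is to verify first.

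Three stronger readings are tempting, and the documents do not support them.
- *Enterococci count as a major criterion only with a focus.* They do not, because the persistent-growth route is open without one. Evidence of infection from surgery or autopsy also establishes a case without blood cultures.
- *About a third of enterococcal cases are misclassified.* The 8 of 24 counts rule combinations with equal weight. The documents give no endocarditis incidence, organism mix or culture timing, and the count falls to 1 of 24 under the printed *or*.
- *The endocarditis rate is wrong by a known amount.* The outcome is a single rate, not split by class, and most shifts may leave it unchanged.

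It can also be said that independent CEC members would notice the oddity and use judgement. That lowers the risk, but coding would then depart from the text that sites and CEC are both told to apply.

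**Conclusion.** The point holds as a minor wording fault in an event definition. As written, the entry gives more weight to an explained enterococcal bacteraemia than to an unexplained one, contrary to the exclusion logic elsewhere in the protocol, and it appears to be an inverted word.

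Its reach is limited to one organism, to cultures that miss the persistent-growth route, and to one of 13 descriptive additional outcomes. Within that group the class changes in 8 of 24 combinations each way under the *and* reading and 1 of 24 each way under the literal *or*. The size of any effect on the reported rate cannot be derived from the documents. Neither primary endpoint is affected.

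The conclusion assumes the ordinary meaning of a primary focus. The counts also assume that a prosthetic valve meets the predisposition criterion. The conflict between the definite and possible rules does not depend on either assumption; it is visible in the text itself.

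**What to change.** Check the enterococcus line against reference 55, which the protocol names as its source, and change *presence* to *absence* unless that source shows otherwise. In the same edit to Appendix V:
- change *cultures or blood samples* to *cultures of blood samples*, so that the 12-hour interval clearly applies;
- reconcile the mixed rule for definite endocarditis with the rule for possible endocarditis.

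In SAP section 7.9.3, item 6, state whether code 163 alone or codes 163 and 164 together count as events. Ask the CEC to re-check any enterococcal event already coded.

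The cost is a few words in Appendix V, one sentence in the SAP and a note to the CEC. No new data collection is needed.
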